7.1. Table of Events

Table 3. Schedule of activities and procedures for a randomized clinical trial

Procedure		Phone screening	Visit 0 baseline	Visit 1 Tx visit	Visit 2 2-week FU	Visit 3 4-week FU online
Docuit a Cample of	Informed consent	Х	Х			
Recruit a Sample of Patients	Eligibility assessments	Х	Х			
Patients	Enrollment and randomization		Х			
Treatment	Administer regimens			Χ		
Climinia Annound	Depressive symptoms		Х		Х	
Clinician-Assessed Measures	DSM-5 Diagnoses		Х			
iviedsules	Anhedonia symptoms		Х		Х	
Cafat	Review concomitant meds.		Х	Х	Х	Х
Safety	Suicidality assessment		Х	Χ	Х	
Monitoring	Assessment of AEs		Х	Х	Х	Х
	anhedonia scores		Х		Х	Х
Patient Reported Measures	depression and anxiety scores		Х		Х	Х
	Stress scores		Х		Х	Х
	Rumination scores		Х		Х	Х

^{1, 2, 3, 4, 5} Footnotes that list and define the measures of interest are used here.

Screening

Participants that request to be in the experiment will provide verbal, documented consent to undergo a phone screening to assess that the participant meets exclusion/inclusion criteria. Participants who are initially deemed initially eligible due to meeting criteria for 5 or more MDD symptoms within Module A of the MINI will be invited to enroll within two weeks of phone screen date.

At the initial in-person visit, participants will provide written consent before completing additional assessments to confirm eligibility and for exploratory analyses. Self-report clinical assessments will be completed on REDCap while being monitored: Inventory of Depression and Anxiety Symptoms (IDAS; Watson et al., 2007); Behavioral Activation System and Behavioral Inhibition System (BIS/BAS; Carver and White 1994), Temporal Experience of Pleasure Scale (TEPS; Gard, Gard et al. 2006), the State-Trait Anxiety Inventory (STAI; Spielberger 2010), and Ruminative Responses Scale (RRS; Nolen-Hoeksema, Larson et al. 1999). Participants will also undergo clinician-administered assessments that will be entered onto REDCap: the Mini International Psychiatric Interview for the DSM-5 (MINI; Sheehan et al., 1998), Hamilton

Version 2 19 September 2022

Protocol Number <#>

Depression Rating Scale (HDRS; Williams, 1988), Snaith- Hamilton Pleasure Scale — Clinician Administrated (SHAPS-C; Ameli et al., 2014), Columbia-Suicide Severity Rating Scale (C-SSRS; Posner et al., 1999). Eligibility for the study is determined by a MINI diagnosis of MDD, exclusion based on a present severe substance use disorder, a present diagnosis of anorexia nervosa, and meeting criteria for current active psychosis. In addition, participants must not have active suicide risk as determined by the C-SSRS (see Inclusion/Exclusion criteria above). In the event that a participant has active plans to commit suicide, an adverse event is recorded, an acute psychiatric assessment is conducted by our medical monitor, [name], who is a clinical psychologist at UNC-CH, and participation is terminated.

Enrollment

After providing written informed consent, further clinical assessments will be conducted (e.g., clinician-administered depression assessment, MINI diagnostic assessment) to confirm eligibility for enrollment.

7.2. Study Visits

Following an eligible phone screen, participants will be scheduled to come in for the first in-person visit within two weeks of the screen. At the session, participants will provide written consent to participate in the study. They will undergo clinician-administered assessments: Hamilton Depression Rating Scale (HDRS), the Snaith-Hamilton Pleasure Scale (SHAPS-C), the Mini International Neuropsychiatric Interview for DSM-5 (MINI) and the Columbia-Suicide severity Rating Scale (C-SSRS). Exclusion criteria for severe SUD, AN, or current psychotic symptoms will be determined from the MINI. In addition, the participant must not have suicide intent as determined by the C-SSRS. At this visit, participants will also complete a reward-related decision-making task (S-EEfRT) during EEG collection. Participants will also complete self-report questionnaires on psychological symptoms.

At the intervention visit, which will occur within one week of the baseline visit, all participants will complete a single-session 90-minute BA treatment. During the second half of the intervention visit, stimulation will occur for a duration of 30 minutes. Participants will be randomized to receive either delta-beta tACS or an active sham stimulation. The C-SSRS will also be administered.

The third session occurs approximately two weeks after the intervention session. At the session, the HDRS, SHAPS-C and C-SSRS will be administered. Participants will complete a behavioral task while EEG data are collected and self-report questionnaires on psychological symptoms.

7.3. Final Visit

Four weeks after their participation in the intervention visit, participants will be emailed a link to complete self-report questionnaires to assess clinical outcomes through REDCap, a secure database web-platform.

7.4. Phone Contacts

N/A

7.5. Follow-Up Contact

N/A

7.6. Early Discontinuations

Data to be Collected If participants elect to withdraw from the study, the reason for discontinuation will be documented. No further follow-up data will be collected.

Criteria for Intervention Discontinuation

The study intervention (i.e., 90 minutes of BA with final 30 minutes of stimulation) will be discontinued for the following reasons:

- Any clinical adverse event (AE), laboratory abnormality, intercurrent illness or other medical condition, or situation occurs such that continued participation in the study would not be in the best interest of the participant.
- The participant meets any exclusion criteria (either newly developed or not previously recognized).

7.7. Enrollees May Drop Out

Participants are free to withdraw from participation in the study at any time upon request.

The reason for participant discontinuation or withdrawal from the study will be recorded with the participant files. Participants who sign the informed consent form and are not randomized will be replaced. Participants who sign the informed consent form, are randomized, and receive the full or part of the study intervention, and subsequently withdraw from the study, are withdrawn from the study, or discontinue the study will not be replaced.

8. Statistical Analysis Plans

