If required by the IRB, the master protocol document, informed consent form(s), recruitment materials, and all participant materials will be submitted to the *Scientific Review Committee* (SRC) prior to IRB review (research.unc.edu/clinical-trials/src).

The statistical analysis plans will be consistent with guidance in CONSORT Statement [1] or STROBE Statement [2], ICMJE recommendations [3], the 2016 and 2019 statements of the American Statistical Association [4,5], and recommendations in Nature [6,7].*

All personnel involved in the conduct of this study have completed human subjects protection training.

^{* [1]} www.consort-statement.org

^[2] www.strobe-statement.org

^[3] www.icmje.org

^[4] Wasserstein RL, et al. (2016), The ASA's Statement on p-Values, The American Statistician, 70:2, 129-133

^[5] Wasserstein RL, et al. (2019), Moving to a World Beyond p < 0.05, *The American Statistician*, 73:sup1, 1-19

^[6] Amrhein, et al. (2019) Scientists rise up against statistical significance, Nature 567, 305-307

^[7] Editorial (2019) It's time to talk about ditching statistical significance: Looking beyond a much used and abused measure would make science harder, but better. *Nature* 567, 283-283.

Table of Abbreviations

AE / SAE	adverse event / serious adverse event
	•
ANOVA	analysis of variance
BA	Behavioral activation
BADS	Behavioral Activation for Depression Scale
BIS/BAS	Behavioral Inhibition System / Behavioral Activation System questionnaire
CFR	U.S. Code of Federal Regulations (www.eCFR.gov)
CT.gov	ClinicalTrials.gov website
C-SSRS	Columbia Suicide Severity Rating Scale
DSMB	data and safety monitoring board
DSM-5	Diagnostic and Statistical Manual of Mental Disorders (5 th Edition)
ECT	Electroconvulsive therapy
EEG	Electroencephalography
FDA	U.S. Food and Drug Administration (www.fda.gov)
GCP	good clinical practice
GLP	Good Laboratory Practices
GMP	Good Manufacturing Practices
GLMM	Generalized linear mixed model
GVS	galvanic vestibular stimulation
HDRS	Hamilton Depression Rating Scale
HIPAA	U.S. Health Insurance Portability and Accountability Act (www.hhs.gov/hipaa)
ICH	International Council for Harmonization (www.ich.org)
ICMJE	International Committee of Medical Journal Editors (www.icmje.org)
IDAS	Inventory of Depression and Anxiety Symptoms
IRB	institutional review board
MDD	Major depressive disorder
MDE	Major depressive episode
MINI	Mini International Neuropsychiatric Interview
MPD	master protocol document
N	number of enrolled participants

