5.1. Numbers of Participants

5.1.1. Number to be screened: $n \le 80$

5.1.2. Number to be enrolled: Our target sample size is N = 40.20 participants will be enrolled in the BA + tACS condition and 20 will be enrolled in the BA + active sham condition. Conservatively, we may enroll up to 80 participants, but a potentially substantially high number of people may not meet criteria for MDD as assessed by the MINI at the baseline visit.

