5.6. Randomization and Concealment

[name], a [name] Lab member, will oversee the randomization of 40 6-digit codes, which will be used by the experimenters. These codes are directly linked to which treatment participants receive (sham/placebo or 10 Hz tACS at 1 mA) and will be entered into the MATLAB script. In addition, 10 codes will be generated in the event that a participant is randomized but discontinues the study. Data will be collected until we reach out target of 40 participants, but there will be no bias towards completion for the different arms (in the unlikely event that one of the arms has more dropout than the others). The assignment of each participant cannot be determined by looking at the codes (e.g., codes are not sequential, code assignment is not based on "odd" or "even" numbers). Thus, the study is both randomized and concealed by virtue of using random numbers generated by a computer. [name] has no other responsibility in the study other than providing these randomized codes. If [name] leaves the [name] Lab, another equivalent researcher who does not work with human participants will perform this task.

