Exploratory analyses are planned only if effects are seen on depressive symptoms (Aim 1). If so, we plan to explore the potential effects specific to anhedonia symptoms. Treatment response will be calculated as the change in anhedonia (SHAPS-C) scores from pre- to post-treatment. A two-way analysis of variance (ANOVA) will be performed using within-participant factor of time (before or after treatment) and between-participant factor stimulation type (delta-beta tACS, active-sham). We hypothesize to find an interaction between time and stimulation type. Post hoc differences will be investigated. We hypothesize that the predicted interaction will be driven by a decrease in anhedonia symptoms for delta-beta tACS compared to the active-sham.

Further, we will conduct exploratory generalized linear mixed models will be conducted to examine potential confounds on treatment effect (e.g., age, sex, baseline non-anhedonic depressive symptoms).

Exploratory analyses with anhedonia symptoms will not be conducted if effects for overall depressive symptoms (Aim 1) are not found.

Planned Interim Analyses

No interim analyses will be performed.

The experiment proposed here will utilize a parallel arm design, and primary analyses will use a repeated-measures ANOVA with one within-participant factor (before and after treatment) and one between-participants factor (deltabeta, placebo). With an average effect size of 0.286 partial-eta square estimated from existing literature on single session BA, we estimate that we need at least 15 participants per group to achieve 80% statistical power. Using a conservative estimate of 0.5 correlation between estimates, we still reach ~99% power with 40 participants (Figure 3). Data will be collected until we reach 40 participants. Given the similarity in stimulation methodology between the current experiment and our previous experiment (Riddle et al., 2021), we anticipate adequate levels of power for hypothesis testing with 40 participants. Moreover, other studies of combined psychotherapy and stimulation have reported similar sample sizes (Neacsiu et al., 2022).

[figure not shown]

Figure 3. Power analysis for impact of BA + tACS on depressive symptoms with ANOVA.

10. Data Capture and Database Management

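### Replacement rules in Sections 5.6 and 7.7 do not fit together as written, the target of 40 is undefined, and Aim 1 names no analysis set or primary missing-data method

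*Combined protocol and SAP*

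**What the plan says.** **Replacement.** Section 7.7 replaces people who consent but are not randomised. Those who "are randomized, and receive the full or part of the study intervention" and then leave, or who "are withdrawn from the study, or discontinue the study will not be replaced", are the group it bars from replacement. It gives no rule for people randomised but never treated. Section 5.6 prepares 40 codes and adds that "10 codes will be generated in the event that a participant is randomized but discontinues the study".

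**The number 40.** The abbreviations table defines N as "number of enrolled participants". The synopsis sets N = 40, assigned 20 and 20, and Section 5.1 repeats the split: "20 will be enrolled in the BA + active sham condition". Section 5.6 also makes 40 a stopping point ("Data will be collected until we reach out target of 40 participants"), as does the sample size text ("Data will be collected until we reach 40 participants"). The synopsis expects at least 30 enrollees with complete data.

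**Analysis.** Section 8.3 plans, for Aim 1, a two-way ANOVA of HDRS before and after treatment. It names no analysis set. Section 7.6 collects no follow-up after withdrawal. Section 8.1 says that strategies for incomplete data will be set in advance and that alternative methods will feature in sensitivity analyses, but it names none. The Aim 1 sensitivity analysis in Section 8.3 concerns anxiety symptoms, and its mixed models are exploratory checks on confounders.

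**The concern.** A participant who is treated and then lost falls under both sections. Section 7.7 says not to replace that person; Section 5.6, as worded, supplies a spare code. Who is randomised and when collection stops therefore depend on which section staff follow.

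The gap carries into the primary analysis. A two-time-point ANOVA needs both HDRS values, so with no data after withdrawal it becomes a complete-pair analysis by default. Section 5.6 recognises possible imbalance ("in the unlikely event that one of the arms has more dropout than the others"). If loss differs by arm and is related to baseline or to change, the complete-pair comparison is biased, and filling the slot with a new participant does not repair it. Section 8.1 says the plans will be finalised before data collection, so these rules should not be left until dropout has been seen.

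**Working it through.** **1. The two rules by group**

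| Group | Section 7.7 | Section 5.6 |
|---|---|---|
| Consented, not randomised | Replaced | No code used |
| Randomised, untreated, left | No rule | Spare code |
| Randomised, treated in full or part, left | Not replaced | Spare code, as worded |

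The second row is a gap and the third a conflict. Followed literally, Section 5.6 allows 40 + 10 = 50 randomised. If 40 means participants with data and loss is 25%, 40/0.75 = 53.3, so 54 would be needed, more than the codes available. Fifty codes give 40 with data only if loss is 20% or less (50 × 0.80 = 40).

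**2. The plan's power**

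Inputs from the sample size text and Section 8.1: partial eta-squared 0.286, correlation 0.5, N = 40, alpha 0.05.

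- f² = 0.286/(1 − 0.286) = 0.4006, so f = 0.633. In SD of change, the arm difference is d = 2f = 1.27.
- Noncentral F with 1 and N − 2 df. The form λ = f² × N × 2/(1 + 0.5) = 21.4 gives power 0.9945 at N = 40, which reproduces the stated figure of about 99%. The form λ = f² × N = 16.0 gives 0.974.
- With 30 pairs, λ = f² × N = 12.0 gives 0.917. The range is 0.90 (λ = f² × (N − 2)) to 0.97 (the first form).
- The difference detectable with 80% power is 0.91 SD at 20 + 20 and 1.06 SD at 15 + 15, both below 1.27.

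**3. Bias from loss**

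The documents give no loss rates by arm and no mechanisms, so those used here are assumptions. Baseline and week-2 HDRS are taken as bivariate normal with correlation 0.5, loss is logistic in the stated variable (slope per SD), and there are 2,000,000 simulated participants per arm.

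- Complete-pair bias in an arm = rate/(1 − rate) × mean deviation in change of those lost.
- Likelihood estimate of the week-2 mean = completers' week-2 mean + b × (baseline mean of all − baseline mean of completers), where b is the slope of week 2 on baseline.

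| Loss depends on | Slope | Loss by arm | Complete pairs | Likelihood model |
|---|---|---|---|---|
| Baseline | 1 | 25% v 0% | 0.11 | 0.00 |
| Baseline | 1 | 20% v 10% | 0.04 | 0.00 |
| Change | 1.25 | 20% v 0% | 0.20 | 0.16 |
| Change | 1.25 | 20% v 10% | 0.10 | 0.08 |
| Part of change unrelated to baseline | 1.25 | 20% v 0% | 0.18 | 0.18 |

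Values are absolute, in SD of change. Checks by the formula: in the first row those lost differ by 0.32 SD, and 0.25/0.75 × 0.32 = 0.107; in the third they are 0.81 SD worse, and 0.20/0.80 × 0.81 = 0.203. Over correlations 0.3 to 0.7, the first row runs from 0.127 to 0.083 for complete pairs and stays at 0.00 for the model. The third row stays at 0.203 for complete pairs and runs from 0.139 to 0.176 for the model.

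**4. Shift needed to offset what remains**

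Shift = remaining bias/loss rate. Change-dependent: 0.158/0.20 = 0.79 SD. Unrelated to baseline: 0.175/0.20 = 0.88 SD. At slope 2 the shifts are about 1.05 and 1.13 SD, so a range capped at 1 SD would be too short.

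**5. Properties of the mixed model**

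- SE ratio to complete pairs, with 15 of 20 pairs per arm: √[(0.75/15 + 0.25/20)/(1/15)] = 0.968, a gain of about 3%.
- With complete data, its arm-by-time term is the difference in mean change, as in the planned ANOVA. The test matches only with N − 2 df. Referring the statistic to the normal value 1.96 turns a nominal 5% into 5.7% (38 df) or 6.0% (28 df).

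**The case against.** The strongest reply is that Section 7.7 already limits the spare codes. It settles the unrandomised and the treated and leaves open only those randomised but untreated. Such people can exist, since Table 3 places randomisation at the baseline visit and treatment follows within a week. On that reading the defect is loose drafting in Section 5.6, and one sentence cures it. The reading is reasonable, so the point is not that the sections cannot be reconciled. But Section 5.6 does not state the limit, and its wording covers treated participants.

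The bias figures also rest on assumed rates and slopes. The part that the model removes completely, 0.04 to 0.11 SD, is small beside the standard error of the arm difference, √(2/20) = 0.32 SD at 40 pairs. That is fair, and it limits how strongly the change can be urged.

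Four stronger readings are not supported:

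- **Randomisation is timed inconsistently.** Section 7.2 mentions randomisation in its intervention-visit paragraph, but the sentence describes the arms. Similar wording appears elsewhere with no timing meaning.
- **The plan expects to lose 10 of 40.** The 30 is a minimum, and the synopsis gives it just after an enrolment ceiling of 80. The base may not be 40.
- **Refilling would favour one arm.** Section 5.6 says, loosely, that completion will not be biased towards either arm.
- **Mixed models are absent from Aim 1.** They are planned, but only as exploratory checks on confounders.

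**Conclusion.** The concern holds in a limited form. As worded, the replacement rules conflict for treated participants who leave and are incomplete for those randomised but untreated. Forty has two meanings, and Aim 1 has neither an analysis set nor a primary missing-data method. If the base for the 30 is 40, up to 10 participants could lack complete data, which is an upper bound on missing HDRS pairs.

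The bias is conditional and moderate: 0.04 to 0.11 SD of change under the assumed baseline-dependent loss, all removable, and 0.10 to 0.20 SD under the other two mechanisms, of which most or all would remain. It is zero if rate and mechanism are the same in both arms. A reader might infer that the trial is underpowered on this account. The figures do not show that: at the plan's own effect, power is still about 0.92 with 30 pairs. Whether that effect is credible is a separate question.

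**What to change.** 1. Reconcile Sections 5.6 and 7.7, the synopsis and the sample size text to one replacement rule. Say whom the spare codes are for, report their use by arm, and state whether 40 means randomised or with data.
2. Make the Aim 1 primary analysis all randomised participants by assigned arm, using a likelihood-based mixed model of baseline and week-2 HDRS with time, arm, arm-by-time and unstructured covariance. Specify small-sample degrees of freedom (for example Kenward-Roger, which gives N − 2 with complete data), so that the test equals the planned ANOVA interaction when nothing is missing.
3. Keep the complete-pair ANOVA as a sensitivity analysis. Add a tipping-point analysis that shifts missing week-2 values by arm, extended until the conclusion changes rather than capped at 1 SD. This gives content to the commitment in Section 8.1.

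The cost is a short amendment, SAP wording and some extra analysis, with no additional patients. The gain in precision is small (about 3% in SE in the 15-of-20 case). The model leaves most or all change-dependent bias, which the tipping-point analysis can only bound.

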8.1. Strategies that Apply to all the Aims

All testing described below assumes a significance threshold of p = 0.05. Analyses will be deemed to be statistically significant if the p-value is less than this threshold. An analysis that does not exceed this threshold will be considered inconclusive.

There may be additional covariates included in the analysis. Data will be assessed for normality and, if deemed necessary, corrective procedures will be applied (e.g., log normalization). Based on our previous dataset, we expect that the variables used here will be approximately Gaussian. However, if the distribution of a variable displays a skewed tail and a test for normality fails, then it is justified to use a corrective procedure. This correction will be applied upon consideration of the variables themselves, and not based on the result of the intended analysis.

Human studies are prone to drop-out, missing data, and interval-censored values. The reasons for drop outs, missing / censored data values, and protocol departures will be documented in the database. Best practices for dealing with incomplete data will depend on the documented causes of those occurrences.

The analysis plans will include outcome-dependent exploratory analyses to generate new hypotheses.

To help ensure replicability of the research, the analysis plans will be reviewed and finalized prior to collection of data (*a priori*). For each specific aim, the analysis plans specify detailed steps for obtaining estimates of the population parameters of interest (e.g., treatment effects) and for making inferences.

- Human studies are prone to drop-out, missing data, and interval-censored values. The reasons for drop-outs, missing / censored data values, and protocol departures will be documented in the database. Best practices for dealing with incomplete data will depend on the documented causes of those occurrences. In the analysis plans established a priori, the strategies for coping with incomplete data will be based on anticipated causes. Alternative methods for dealing with incomplete data will play important roles in the sensitivity analyses.
- All hypothesis tests yielding large p-values will be reported as being inconclusive. For all sample sizes, all hypothesis test procedures are (by design) incapable of establishing that the null hypothesis is true.
- If p-values are computed they should be reported to several decimal places without categorizing or dichotomizing the p-value; that is, the words "significant" and "non-significant" should be avoided. The p-value should be reported and interpreted as a continuous measure indicating the availability of information against

19 September 2022

the (null) hypothesis being tested. The available amount of information against the null hypothesis is equal to the Shannon Information S-value, and the p-value = $(\frac{1}{2})^{S-value}$. Smaller p-values (larger S-values) indicate greater amounts of available information. Larger p-values indicate a lack of information; e.g., if p = 1 then the S = 0. If p = 0.03125 then S = 5 which indicates a result that is as-surprising-as observing 5 'heads' in a row when flipping a coin 5 times to test whether it is a fair coin. Due to lack of information, large p-values cannot be used to draw any conclusions as to whether the tested null hypothesis is true or false. Lack of availability of evidence of an effect is not evidence of a lack of effect.

• The proposed statistical analysis strategy acknowledges that no p-value can reveal the plausibility, presence, truth, or importance of an association or effect --which is consistent with the statements of the American Statistical Association [4,5], the recommendations in Nature [6,7], and guidance, such as the CONSORT Statement [1], STROBE Statement [2], and ICMJE guidance [3].[†]]

